5 Health-related biomedical or behavioral outcome is defined as the pre-specified goal(s) or condition(s) that reflect the effect of one or more interventions on human subjects’ biomedical or behavioral status or quality of life. Examples include: positive or negative changes to physiological or biological parameters (e.g., improvement of lung capacity, gene expression); positive or negative changes to psychological or neurodevelopmental parameters (e.g., mood management intervention for smokers; reading comprehension and /or information retention); positive or negative changes to disease processes; positive or negative changes to health-related behaviors; and, positive or negative changes to quality of life.

CS18.0 * Based on the above information, does this study meet the NIH definition of a clinical trial? Yes No

If Yes, click Save and then Click Here For Study Team's CITI Training Records . Please ensure all personnel's training is up to date

[reviewer notes-]

Section 1 - Study Objective, Specific Aims, Background and Significance

1.1 Objective: What is the overall purpose of this research study? (Limit response to 1-2 sentences.)The objective of this study is to assess the efficacy of minimally invasive autologous fat transfer at the amputation sites and the modulation of pain at the respective sites. We hypothesize that autologous fat grafting can provide a minimally invasive therapy facilitated by enabling technology of specialized instrumentation to effectively mitigate pain syndromes at amputation sites, by introducing volume stable

Section: Section 1 - Objective, Aims, Background and Significance

subcutaneous tissue over bony prominences and peripheral nerve trunks, thereby avoiding surgical revisions and preserving limb length. The premise of this study is that we will compare two minimally invasive techniques as an alternative to invasive operations, with the understanding that this therapy does not preclude more invasive procedures in the future. We further hypothesize that enriching the fat graft with autologous adipose stromal cells utilizing the Tissue Genesis Cell Isolation System (CIS), a regenerative medicine approach, will lead to improved retention of the fat graft over time and result in a more favorable outcome.

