- 1.2 Specific Aims: List the goals of the proposed study (e.g., describe the relevant hypotheses or the specific problems or issues that will be addressed by the study).1) Treat painful amputation sites in 30 patients with fat grafting to provide additional subcutaneous tissue padding over bony structures and nerve trunks. Limb anatomy and healing of the graft over time, along with stability/persistence of the new tissue, will be assessed by high resolution CT scanning with 3D reconstruction. Patients will be followed for 24 months after treatment to define long term outcomes. The primary outcome measures will be pain at the amputation site and improved ability to tolerate a prosthesis. Patients will be randomized to receive either standard fat grafting (15 patients) or cell enriched fat grafting (15 patients) utilizing the Tissue Genesis Cell Isolation System (CIS). Patients will be enrolled who have pain at an amputation site that limits function and/or interferes with the ability to use a prosthesis.2) Assess biologic properties of the cells within the fat graft and correlate with clinical outcomes. This will include adipose stem cell yield per volume of fat tissue, cell proliferation, capacity for adipogenic differentiation, lipolysis, and cell sub-population analysis by multiparameter flow cytometry. Results of these assays will be correlated with graft volume retention to search for predictors of good clinical outcome that are related to variation in adipose biology between subjects.3) Measure quality of life in patients before and after autologous fat grafting using validated psychosocial measures. This will include, among other tools, SF 36, the Beck inventory, and instruments designed for assessing limb function.

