
performed as described in SOPs 2005-13-R5 [SOPs are Attached] and 2008-02-R0. The acceptable endpoints are: AO viability \geq 50%; Endotoxin levels $<$ 5EU/kg of recipient ideal body weight, cell yields \geq 1E+05 total SVF cells per mL of adipose stroma and gram stain negative. The determinations will be recorded in triplicate. All handling and procedures with the lipoaspirates and isolation of the SVF are handled in sterile areas and all personnel are appropriately gowned and gloved as well as all laboratory instruments (pipettes, etc.) have been appropriately sterilized/cleaned. c. The released adipose stromal vascular fraction preparation will be transported back to the operating room. The concentrated autologous stromal vascular fraction cells will arrive back in the operating room close to the time that the standard fat graft preparation process is completed. It is anticipated that the time required for preparing the Autologous Stromal cells concentrated fat graft will add no more than 30 minutes to the overall operating time compared to Autologous Standard fat graft processing. d. The Standard graft material and the stromal vascular fraction cells will be mixed and subsequently injected into the amputated stump a target concentration of $2.0 - 3.0 \times 10^6$ stromal vascular cells/ml of injected fat graft is desired in this study. However, we recognize that there will be significant variation in cell yield between patients, as well as variation in required graft volumes. The actual cell dose for each subject will be collected to the intraoperative source document. The procedure for combining the SVF with the lipoaspirate prepared in the operating room will be performed inside the sterile operating room by [name] or a co-investigator who is specifically trained in the techniques of fat graft processing using the [name] method as well as this cell-enrichment technique of combining SVF with lipoaspirate. i. To manually combine the standard fat graft material and the SVF suspension (device output), each of the syringes will be connected via luer to luer lock. The contents of the lipoaspirate syringe are transferred to the SVF syringe and the cell suspension will be injected slowly back and forth between the two (2) syringes. The final 1 mL SVF-fat graft syringe is now considered cell-enriched and ready for injection into the subject. ii. It should be noted that in the event of fat harvest from both abdomen and thigh, abdominal fat grafts will be combined with abdominal fat SVF and thigh fat grafts will be combined with thigh fat SVF. Fat Graft Placement: The plastic surgeon will use the specially designed hollow injection cannulas (smaller diameter cannulas with varied shapes and tip sizes specifically made to deliver smaller amounts of fat) to fill the desired areas with the designated portion of fat. Incisions for cannula sites average less than 5 mm. The [name] Cannula System is not experimental and is commercially available in the United States and in compliance with Federal regulations for surgical instruments. A maximum fat graft volume, to include control grafts and SVF-concentrated grafts, of 300mL will be injected. The graft volume necessary to treat the stump site will be determined by the clinical judgment of [name]. They are plastic surgeons who have significant experience in fat grafting techniques. In addition, previous high-resolution 3D CT scans will be used to help determine the fat volume needed to treat. As is standard of care for fat grafting, the fat will be injected in small 3mL syringes to prevent excessive ischemia that may otherwise be seen with larger graft volumes. If additional SVF

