
derived stem cells (ASC) Proliferation: Cellular proliferation of preadipocytes will be assessed with the CyQUANT Cell Proliferation Assay Kit (Invitrogen, Carlsbad, CA) at 48 and 96 hours. Media will be changed every 48 hours. Adipose derived stem cells (ASC) Differentiation: To assess the potential of the ASC to differentiate into the adipogenic cell type within the HA gels, cells will be treated plating media containing 0.2 nM dexamethasone, 0.5 uM insulin, 0.2 nM triiodothyronine, antibiotics, and 540 uM IBMX in addition to their current media. To confirm adipogenesis, lipid inclusions cells will be confirmed by staining with Oil Red-O. Additionally, protein expression of PPAR gamma and FABP4 will be determined using western blot analysis, and RNA expression of these adipogenic markers will be determined using PCR. Flow Cytometry Adipose derived stem cells (ASC) characterization: We will characterize ASC from each patient for stem cell surface antigens using flow cytometry. Passage zero preadipocytes isolated (as described above) from the abdominal subcutaneous tissue will be divided into aliquots of 5x10 (5) cells and stained with selected monoclonal antibodies (mAbs) against progenitor cell surface markers. The antibodies include mAbs against CD34, CD45, CD90, CD133, CD105 and CD166. Rationale for these surface markers includes the following: 1) markers that are routinely examined for bone marrow stem cell markers, and have also been examined as ASC markers and 2) will be able to discern stem cell purity by testing for these markers. The cells will be incubated with mAbs C, and washed in PBS. At least 100,000 viable cells will be incubated for 30 min with 7AAD(-) staining in each sample will be acquired and analyzed using a FACS Aria fluorescence-activated cell sorter (Becton-Dickinson).

2.6.1

Will blood samples be obtained as part of this research study?

* Yes *If submitting a protocol for expedited review, it should be clear that the planned blood draws are within the parameters described here:

<http://www.hhs.gov/ohrp/policy/expedited98.html> (see Expedited Research Category #2)

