2.15.3 Will biological specimens be stored without identifiers or linkage codes? *

[reviewer notes-]

Section 2 - Research Design and Methods

2.16 Will research participants be asked to provide information about their family members or acquaintances?

* No

2.16.1 Describe what information about the third party will be obtained from the participant:

2.16.2 If the information about the third party is of a private nature, can the identity of the third party be readily ascertained or associated with this information?

*

Describe the private information that will be collected and recorded about the third party:

[reviewer notes-]

Section 2 - Research Design and Methods

Section: Section 2 - Research Design and Methods

2.17

What are the main outcome variables that will be evaluated in this study?

Primary outcomes: Improvement of pain at the amputation site, improved ability to tolerate a prosthesis, and generation of a stable volume of adipose tissue at the amputation site (as measured by clinical assessment by rehabilitation sciences and prosthetics team, quality of life measures, and high resolution imaging). This will be compared between the standard fat grafting group (n=15) and the adipose cell enriched fat grafting group (n=15). Secondary outcomes: Local and systemic complications resulting from fat graft procedure (infection, fat necrosis, hematoma, seroma); basic assays of adipose cell behavior to elucidate the functional properties of adipose cells used for grafting, with correlation to outcomes.

2.18

Describe the statistical approaches that will be used to analyze the study data.

* Addressed below:

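### Aim 2 gives no arm term for correlating cell assays with graft retention, and its flow cytometry is tied to abdominal fat although the graft may be thigh fat

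*Combined protocol and SAP*

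**What the plan says.** **Analysis.** Section 1.2, aim 2, sets out to assess the cells within the graft. It names five types of assay: stem cell yield, proliferation, adipogenic differentiation, lipolysis and sub-population analysis by flow cytometry. It then states: "Results of these assays will be correlated with graft volume retention to search for predictors of good clinical outcome". Section 2.17 lists as a secondary outcome "basic assays of adipose cell behavior to elucidate the functional properties of adipose cells used for grafting, with correlation to outcomes". Section 2.18 covers paired t-tests for pain and imaging, repeated-measures analysis of variance for change over time, and a composite functional score compared between groups. It gives no model, arm term or imaging visit for the assay correlations, and no rule on the number of assays.

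**Arm and retention.** Section 1.1 hypothesises that enrichment "will lead to improved retention of the fat graft over time and result in a more favorable outcome". Only the enriched arm receives added stromal vascular fraction (SVF) cells. Section 2.6, item d, expects that "there will be significant variation in cell yield between patients, as well as variation in required graft volumes" and adds: "The actual cell dose for each subject will be collected to the intraoperative source document". That recorded dose is not named in any analysis.

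**Tissue.** Section 2.6 says that fat is usually harvested from the abdomen or thighs. Item d.ii provides for harvest from both sites: "abdominal fat grafts will be combined with abdominal fat SVF and thigh fat grafts will be combined with thigh fat SVF". The flow cytometry paragraph in the same section reads: "Passage zero preadipocytes isolated (as described above) from the abdominal subcutaneous tissue will be divided into aliquots". The stromal cells are isolated from 5-25 cc of lipoaspirate whose harvest site is not stated.

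**The concern.** Retention is the outcome in Aim 2, and by the trial's own hypothesis it differs between arms. A correlation that takes no account of arm leaves that difference in the residual variation and so loses some power. With only 30 patients there is little to spare.

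The tissue question is separate. Aim 2 is about the cells that were grafted. If flow cytometry is done only on abdominal tissue, a patient whose graft came entirely from the thigh either contributes nothing to that analysis or contributes a measurement of other tissue. This cannot be repaired once the lipoaspirate has been used.

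**Working it through.** **Inputs from the documents.** 30 patients, 15 per arm (Section 1.2); alpha 0.05 and an effect size of about 0.9 (Section 2.18, where the 0.8 called beta is read as power).

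**Assumptions, not in the documents.** Within-arm correlation r = 0.5; arm shift d from 0 to 1.5 within-arm SD of retention; share of thigh-only patients 10% to 50%; abdomen-thigh correlation of a flow readout 0 to 0.9.

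**Step 1: the plan's only power figure.** Detectable d = (z for alpha + z for power) × √(2/15).
- One-sided: (1.645 + 0.842) × 0.365 = 0.91.
- Two-sided: (1.960 + 0.842) × 0.365 = 1.02.

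The stated 0.9 therefore reproduces as a one-sided two-group comparison. It concerns soft tissue volume, and it is what thirty patients may detect rather than an expected effect. Nothing is stated for Aim 2. A shift of 0.9 SD is used below as one case among several.

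**Step 2: cost of omitting arm, same slope in both arms.** At 1:1 allocation an unmodelled shift adds d²/4 to a within-arm variance of 1, so the observed correlation is r/√(1 + d²/4). Two-sided power is Φ(√(n − 3) × atanh r − 1.96), with n − 4 in place of n − 3 when arm is in the model. For d = 0.9: 0.5/√1.2025 = 0.456, then √27 × 0.492 − 1.96 = 0.60, and Φ(0.60) is about 72.5%. With the arm term, √26 × 0.549 − 1.96 = 0.84, or 80%, whatever the shift.

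| Shift d | r without arm | Power without arm, formula | Without arm, simulated | With arm, simulated |
|---|---|---|---|---|
| 0 | 0.500 | 81.4% | 83% | 82% |
| 0.5 | 0.485 | 78.6% | 80% | 82% |
| 0.9 | 0.456 | 72.5% | 74% | 82% |
| 1.5 | 0.400 | 59.5% | not run | not run |

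The simulations used 20,000 trials for d = 0 and 0.9, and 8,000 for d = 0.5.

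**Step 3: false positives.** With no true relation and d = 0.9, the simulated error rate is 5.0% without the arm term and 4.8% with it. This is as expected: arm is randomised and the assays are run on unenriched lipoaspirate, so arm and assay are independent.

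**Step 4: what by-arm analysis can deliver.**
- Slope within one arm, n = 15, r = 0.5: Φ(√12 × 0.549 − 1.96) = 48%.
- Interaction test, r = 0.5 against 0: Φ(0.549/√(2/12) − 1.96) = 27%.
- Relation in one arm only, r = 0.5, shift 0.9 SD: about 24% without the arm term, 27% with it and no interaction, 48% for the slope in that arm.
- Number of tests: five assay types at 0.05 give 1 − 0.95⁵ = 23% for at least one false positive if independent. Testing each in both arms makes ten tests, and 1 − 0.95¹⁰ = 40%.

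**Step 5: tissue.** Three statements in Section 2.6 sit side by side: harvest from abdomen or thighs; like mixed with like when both are used; flow cytometry on abdominal cells. They agree for abdomen-only grafts. For a graft from both sites the flow result describes part of what was grafted. For a thigh-only graft the text offers no valid result.
- If the result is missing, n falls. A 10% share leaves 27 patients: Φ(√24 × 0.549 − 1.96) = 77%. A 50% share leaves 15: 48%. The full-sample figure is 81%.
- If ungrafted abdominal tissue were used, r becomes 0.5 × [(1 − share) + share × abdomen-thigh correlation]. This runs from 0.495 (10% share, correlation 0.9; power about 80%) to 0.25 (50% share, correlation 0; power about 26%).

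**The case against.** The strongest reply is that the documents never say the arms will be pooled. They are silent, and an analyst could adjust for arm without departing from the text. The aim is secondary, in a trial that calls itself a pilot, and its wording about searching for predictors already suggests exploration. The loss is also small unless the arm shift is large, and it vanishes if there is none. All of this stands. It limits the point to an unspecified analysis with a modest cost.

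A reader might infer that real predictors in the enriched arm would be missed. With r = 0.6 in that arm and 0 in the other, simulated power is about 32% without an arm term and 70% within the enriched arm alone. The documents do not support resting on that contrast. The one-arm pattern is assumed, and the interaction test would detect it only about 37% of the time. Where the slope is the same in both arms (r = 0.5), splitting by arm cuts power to about 48%.

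A reader might also infer that the yield assay sets the cell dose in the enriched arm, so that slopes must differ. Section 2.6 describes two separate measurements. The assay uses a research sample digested in another laboratory. The dose comes from the cell isolation device, with a target concentration and the option of a second device. A slope difference is plausible but does not follow from the text.

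On tissue, it can fairly be said that Section 2.6 describes no abdominal harvest in a thigh-only patient, so a missing result is likelier than a mismatched one. The conflict is documented for flow cytometry only. That narrows the tissue point but does not remove it.

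**Conclusion.** The concern holds in a limited form. Aim 2 has no stated model, and an arm term is worth including because the trial expects arm to shift retention. If the within-arm correlation is 0.5, the gain is about 8 percentage points of power at a shift of 0.9 SD (74% to 82%), about 2 at 0.5 SD (80% to 82%) and none at zero. Both the correlation and the shift are assumptions. Omitting arm produces neither bias nor extra false positives, so it would be wrong to read the plan as generating spurious predictors.

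The tissue conflict rests on the text alone. As written, a thigh-only patient has no valid flow cytometry result, contrary to the aim of assessing cells within the graft. Its size cannot be fixed because the documents give neither the share of such patients nor how alike the two depots are.

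Neither part touches the primary comparison between arms or safety.

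**What to change.** - **Section 2.18:** for each assay, specify a regression of graft volume retention, at a named imaging visit, on the assay and randomised arm as the main Aim 2 analysis.
- **Exploratory only:** report the arm-by-assay interaction and the by-arm slopes with confidence intervals as estimates. State that power is low at 15 per arm and that these add to the number of tests.
- **Section 2.6, flow cytometry:** replace the abdominal source with lipoaspirate from the depot actually grafted, and record the depot for every patient.
- **Reporting:** state how many assays were tested and label the findings hypothesis-generating.

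The cost is a few sentences of analysis text, a sampling instruction and one recorded item. The arm term uses one degree of freedom, which at zero shift lowers power by about one percentage point (81% to 80% by the formula). No patients, visits or procedures are added. The sampling change helps only patients whose lipoaspirate has not yet been used.
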